3.1. General Design

This study is designed to evaluate the effectiveness of gamma tocopherol for mitigating features of airway inflammation induced by inhaled WSP by examining airway inflammatory cell recruitment and cytokine production, and mucous production,. We anticipate 3 years will be required for completion of study visits for all participants.

Upon successful completion of two screening protocols (one as a general screen to determine eligibility for airway challenge studies and a second to identify those individuals who are deemed “responders” to WSP inhalation, defined as $\geq 10\%$ increase in sputum PMNs following exposure), participants will be enrolled to participate in a randomized, double blinded, placebo-controlled, crossover study consisting of 8 visits. Participants will be randomized to γ T or placebo treatment followed by chamber exposure with WSP. After a 4-week washout period, participants will cross over to the alternate treatment group.

Following randomization to placebo or gamma tocopherol treatment, subjects will return for baseline (V0) and training visits (V1). Participants will consume 1400 mg of γ T-enriched supplement or placebo once daily for 7 days. Participants will undergo WSP exposure (V2), then return the following day for a 24 hour post-exposure visit (V3). After a 4 week wash out period, subjects will present for a review of medical history and adverse events and cross over to the alternate treatment (V4). They will undergo a second WSP exposure (V5) followed by a 24 hour post-exposure visit (V6). Five to 10 days after the exposure, participants will return for a study completion visit (V7).

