3.4. Primary Safety Endpoints

Safety Endpoints: Safety endpoints include respiratory symptoms such as wheezing or shortness of breath requiring albuterol, significant bleeding events, or significant change in blood coagulation markers (PT, aPTT) such that these measurements are outside of normal range, and adverse events (AEs) and severe adverse events (SAEs). Exploratory safety endpoints include GI symptoms with γ T vs Placebo. Adverse event data will be collected through 7 days post study drug treatment for both treatment periods. UNC Chapel Hill Human Research Protection Program Standard Operating Procedures will be followed for reporting adverse events/unanticipated problems to the Biomedical IRB. All SAEs will be reported to the CDER of the FDA as well as to the UNC Biomedical IRB within 24 hours of recognition of the event. Adverse events will be reported to both the FDA and UNC IRB on no less than an annual basis, or when the protocol is completed.

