5.1.4. Visits 2 (Period 1) and 5 (Period 2): WSP exposure

1. Vital signs, oxygen saturation, resting blood pressure
2. GI and WSP Exposure symptom questionnaire
3. Collect symptom diary
4. Urine pregnancy test for females
5. HRV will be collected throughout the entire visit with a Spacelabs monitor. The monitor will be worn until the 24 hours post exposure visit.
6. Spirometry
7. Venipuncture (CBC with differential, serum cytokines, serum C-reactive peptide, lipid panel, LDH, fibrinogen, gT and metabolite levels)
8. 500 μ g/m³ WSP chamber exposure for 2 hours, with intermittent exercise and rest. Subjects will alternate 15 minutes of exercise on a cycle ergometer (intensity needed to achieve 20 L/min/m² BSA determined at baseline visit) with 15 minutes of rest.
9. Symptom questionnaire (immediately prior to exit from the chamber)
10. Spirometry and resting blood pressure (immediately following exit from the chamber)
11. Lunch - low fat meal is provided. The meal must be the same during each exposure.
12. Obtain 30 minute controlled rest HRV, FMD, and LVS (90 minutes post-WSP exposure)

13. Venipuncture (CBC with differential, serum cytokines, serum C-reactive peptide, lipid panel, LDH, fibrinogen) (4 hours post-WSP exposure)
14. GI and WSP Exposure Symptom questionnaire (4 hours post-WSP exposure)
15. Sputum induction (4 hours post-WSP exposure)

5.1.5. Visit 4: Dispense Study Drug (Period 2) (following 4 week washout and at least 1 week prior to V5 Exposure Visit and up to 3 weeks)

1. Review medical history and adverse events
2. Urine pregnancy
3. Vital signs, oxygen saturation, GI symptom questionnaire
4. Dispense study drug
5. Lung function testing for participants who have asthma

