5.1.6. Visits 3 (Period 1) and 6 (Period 2): 24 hours post-exposure

1. Review any adverse events
2. Vital signs, resting blood pressure, oxygen saturation
3. WSP Exposure symptom questionnaire
4. Venipuncture (CBC with differential, serum cytokines, serum C-reactive peptide, lipid panel, LDH, fibrinogen, PT, aPTT, INR, gT and metabolite levels)
5. Spirometry
6. Sputum induction
7. .

At least a 4 week, but no more than an 8 week washout is required between Period 1 and Period 2.

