5.1.7. Visit 7: Study completion, 5-10 days post-exposure

1. Review any adverse events
2. Vital signs, oxygen saturation, symptom questionnaire
3. If the participant has any health symptoms or concerns, they will receive a physical examination and evaluation by a study physician.

We will contact participants 1 month after participation to follow up and ask about health status.

If the participant develops an upper or lower respiratory tract illness between V0 and V1 or between periods, we will postpone the next study visit for a minimum of 4 weeks after resolution of symptoms. In this case, if V1 occurs >1 month from V0, or if V4 occurs >2 months from V3, to prioritize participant safety we will bring the subject in for an additional visit to collect safety labs, perform spirometry, and review interval history.

If the participant has an illness mid-dosing of the gamma tocopherol/placebo or fails to adhere to the dosing regimen, participants will return 4 weeks after they have taken their last dose or 4 weeks after resolution of symptoms. At that visit, gamma tocopherol/placebo will be re-dispensed. To prioritize participant safety we will review interval history. Subjects with an illness during dosing, we will additionally collect safety labs, and perform spirometry.

All subjects with a symptomatic Covid 19 infection will be deferred for 90 days. Baseline spirometry and safety labs will be assessed prior to any gamma tocopherol/placebo dosing and WSP exposure.

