7.1. Definition of Adverse Event (AE) and Serious Adverse Event (SAE)

Adverse events and serious adverse events will be recorded and reported according to 21 CFR 312.32. An adverse event for a given volunteer will be defined as any untoward medical occurrence associated with the use of a drug whether or not considered drug related and will also include failure of any of the safety criteria outlined in section “3.4.”. Additionally, minor upper respiratory tract infections occurring within 96 hours of the exposure will be considered adverse events. Other non-specified clinical illnesses or symptoms, which occur during the treatment period or within 96 hours of each challenge, will also be reported as an AE. Any decrease in lung function or increase in symptom score, as outlined in section “3.4,” will be considered an

adverse event. Any symptoms that induce a volunteer to seek medical attention from any provider during study drug treatment or within 7 days of completing study drug treatment or within 96 hours of challenge will be considered an adverse event. A serious adverse event will also be defined as any event that requires hospitalization or results in life threatening illness or injury, permanent (or likely to be permanent) illness or injury, or death if these events occur during study drug treatment or within 7 days of completing study drug treatment or within 96 hours of challenge (or if the clinical scenario leading up to hospitalization, illness, injury or death begins during study drug treatment, within 7 days of completing study drug treatment or within 96 hours of a challenge).

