7.3. Measures to Minimize Risk

7.3.1. Protections to Minimize Risk of Gamma Tocopherol

Tocopherols may affect coagulation. We will query volunteers for bruising and bleeding prior to enrollment and during the dosing period, and will monitor PT and aPTT values prior to the first dose of study drug and at the end of the dosing period. They may be checked at any time the subjects experiences abnormal bruising. Any participant with an abnormal baseline PT, aPTT or INR will be excluded from receipt of study treatment. Spirometry is performed at regular intervals throughout the γ T dosing period to monitor for any changes in lung function. As to the incidence of gastrointestinal symptoms, we will recommend that γ T supplements be taken with a high-fat meal to promote intestinal absorption of γ T and mitigate many associated diarrhea or bloating. Participants will receive a GI symptom diary to be completed daily while taking the study drug and returned to study coordinators on the morning of the challenge visits (Visit 2 or 5). All female subjects, except those who have had a hysterectomy with oophorectomy, will undergo urine pregnancy testing prior to beginning treatment and prior to WSP exposure. A positive pregnancy test will exclude the subject, and they will be withdrawn if they become pregnant during the course of the study. Study medication, including placebo, will be dispensed by the Investigational Drug Service of UNC Hospitals.

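### In Period 2 the closing visit can fall 1 to 2 days before the 7-day adverse-event window of section 3.4 ends, and two 96-hour clauses in section 7.1 do not match that window

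*Combined protocol and SAP*

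**What the plan says.** **Collection window.** Section 3.4 counts from study drug: "Adverse event data will be collected through 7 days post study drug treatment for both treatment periods".

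**Closing visit.** Section 5.1.7 counts from the smoke exposure: "Visit 7: Study completion, 5-10 days post-exposure". Section 3.1 gives the same interval. V7 is the last visit at which adverse events are reviewed. The only scheduled contact after it is described as follows: "We will contact participants 1 month after participation to follow up and ask about health status".

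**Period 1.** V4 comes after the washout and includes the item "Review medical history and adverse events". On the length of the washout, section 5.1.6 says: "At least a 4 week, but no more than an 8 week washout is required between Period 1 and Period 2".

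**End of dosing.** The course is 7 days, once daily (section 1.3). Study drug may be dispensed 1 to 3 weeks before exposure (sections 5.1.3 and 5.1.5), and the day of the last dose relative to exposure is not given. Section 7.3.1 says that the symptom diary is "to be completed daily while taking the study drug and returned to study coordinators on the morning of the challenge visits". It also places a PT and aPTT check at the end of dosing, and section 5.1.6 draws those tests at V3 and V6, the day after exposure.

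**Definitions in section 7.1.** The section opens with a general adverse-event definition that has no time limit. It then adds clauses:
- Minor upper respiratory infections count if they occur within 96 hours of exposure.
- Unlisted illnesses and symptoms are those "which occur during the treatment period or within 96 hours of each challenge, will also be reported as an AE".
- Medically attended symptoms and serious events count up to 7 days after the end of study drug or within 96 hours of challenge.

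Section 7.1.2 lists gastrointestinal distress and coagulopathy with or without bleeding as protocol-specific events, graded from mild upward, with no 96-hour limit.

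**The concern.** Section 3.4 ties the safety window to the last dose, and the visit that should close it is tied to another event. Nothing in the protocol links the two dates. A site that books V7 at the early end of its permitted range complies fully and may still do the last adverse-event review before the window has ended.

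The definitions raise a second question. A minor illness that starts after 96 hours but within 7 days of the last dose lies inside the section 3.4 window and outside the two 96-hour clauses. Staff could record it or leave it out, each with a section to cite.

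What is at stake is the completeness of the safety record and what the report can claim. Without a change, it cannot say that every participant had the follow-up that section 3.4 describes.

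**Working it through.** The plan gives no derived figure to reproduce. The check is day counting.

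**Inputs**
- Safety window: 7 days after the last dose (section 3.4).
- V7: day v after exposure, v = 5 to 10, which is 6 permitted days (sections 3.1 and 5.1.7).
- 96 hours = 4 days after exposure (section 7.1).
- g = days from last dose to exposure. This is not stated, so g = 0 to 3 is an assumption. Return of the diary on the challenge morning and the coagulation tests at V3 and V6 point to a small g, but do not fix it.

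**Formulas**
- Days covered after the last dose at V7 = v + g.
- Shortfall = max(0, 7 − (v + g)).
- Days of the section 3.4 window left after the 96-hour limit = max(0, 7 − (4 + g)).

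**Period 2 results**

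| g | Shortfall, V7 day 5 | Shortfall, V7 day 6 | Shortfall, V7 days 7–10 | Permitted V7 days that fall short | Window days after the 96-hour limit |
|---|---|---|---|---|---|
| 0 | 7 − 5 = 2 | 7 − 6 = 1 | 0 | 2 of 6 | 7 − 4 = 3 |
| 1 | 7 − 6 = 1 | 7 − 7 = 0 | 0 | 1 of 6 | 7 − 5 = 2 |
| 2 | 0 | 0 | 0 | 0 of 6 | 7 − 6 = 1 |
| 3 | 0 | 0 | 0 | 0 of 6 | 7 − 7 = 0 |

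V7 on day 7 or later covers the window for every g of 0 or more. The earliest V7, at 5 × 24 = 120 hours, is always past the 96-hour limit, so that limit is met by the schedule.

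**Period 1.** V3 is 1 day after exposure. With a washout of at least 4 weeks counted from V3, V4 falls at least 1 + 28 = 29 days after exposure, well past day 7. The window is covered, but by recall: with g = 0, an event on day 7 is asked about at least 29 − 7 = 22 days later.

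**Section 7.1 against section 3.4**

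| Type of event | Limit in section 7.1 or 7.1.2 | Agrees with 7 days after drug? |
|---|---|---|
| General definition | None stated | No conflict |
| Medically attended symptoms | 7 days after drug or 96 hours after challenge | Yes |
| Serious events | 7 days after drug or 96 hours after challenge | Yes |
| GI distress, coagulopathy or bleeding (7.1.2) | No 96-hour limit | No conflict |
| Minor upper respiratory infections | 96 hours after exposure | No |
| Unlisted illnesses or symptoms | Treatment period or 96 hours after challenge | No |

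The mismatch is confined to the last two rows.

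**The case against.** The case against giving this much weight is substantial, and most of it stands.

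- **Coverage.** A reader might infer that the window is missed in both periods. The documents do not support that: V4 reviews adverse events after the whole Period 1 window, and V7 on days 7 to 10 covers Period 2. Section 3.4 does not say that collection stops at V7, participants can reach a study physician at any hour (section 7.3.8), and the 1-month contact falls after the window.
- **Definitions.** A reader might infer that section 7.1 works to 96 hours throughout, or that diarrhoea or bleeding on day 6 without a medical visit is not an adverse event. Neither follows. Medically attended and serious events have the 7-day limit, the general definition has no limit, the 96-hour clauses are worded as additions to it, and section 7.1.2 names GI distress and coagulopathy with or without bleeding without a 96-hour limit. It would also be wrong to say that 3 of the 7 days are lost for every event without medical contact.
- **Consequence.** The bleeding endpoint is limited to significant events, and GI symptoms are exploratory (section 3.4). In the earlier 14-day trial GI symptoms began after the first or second dose, and they resolved during treatment in all but one participant, who withdrew (section 1.3). A daily diary covers dosing. The documents give no reason to expect important events to appear first on days 6 or 7.

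Two things are left. Access to a physician depends on the participant making contact, and the 1-month enquiry is not described as adverse-event collection, so neither amounts to a scheduled review of the final days of Period 2. And the two 96-hour clauses do differ from section 3.4.

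**Conclusion.** The point holds in a limited form. The schedule does not guarantee the Period 2 safety window. The shortfall is 0 to 2 days and depends on an interval that the protocol does not state: 2 of the 6 permitted V7 days fall short if dosing ends on the exposure day, 1 of 6 if it ends the day before, and none if it ends 2 or more days before. Period 1 is covered, with reliance on recall.

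The definitional mismatch concerns only minor upper respiratory infections and unlisted illnesses or symptoms. For these, 3 days of the section 3.4 window lie beyond the 96-hour limit if dosing ends on the exposure day, and 2 if it ends the day before. Because the general definition has no time limit, such events may be classified differently by different staff; the text does not clearly exclude them.

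Sequence is randomised in balanced blocks, so an early V7 should affect both treatments about equally. The harm is incomplete ascertainment and an unsupported statement of follow-up, rather than an evident bias between treatments.

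**What to change.** 1. Reconcile the V7 window with section 3.4 so that V7 falls no earlier than 7 days after the last Period 2 dose. If dosing ends by exposure, a window of 7 to 10 days post-exposure does this for any gap. Sections 3.1 and 5.1.7 both need the change.
2. State in the protocol the interval between last dose and exposure, so that the window can be dated.
3. In section 7.1, align the 96-hour clauses for minor upper respiratory infections and unlisted illnesses or symptoms with the section 3.4 window, as the clauses for medically attended and serious events already are.

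The cost is protocol wording and a narrower V7 window, 4 permitted days instead of 6. No visit or procedure is added. A V4 question dated to the 7 days after the Period 1 course would make the two periods more alike, but it is optional: V4 already reviews adverse events, and the question is not needed to correct an error.

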3.4.1. Criteria for safety prior to initiation of wood smoke inhalation challenge

(Subjects not meeting these criteria the morning of challenge will not proceed with wood smoke inhalation challenge):

1. FEV₁ of at least 75% of predicted (without use of bronchodilating medications for 12 hours) consistent with lung function of persons with no more than mild intermittent or mild persistent asthma.
2. Baseline oxygen saturation of at least 93%.
3. No history of viral respiratory tract symptoms within 4 weeks of challenge.
4. No current symptoms of rhinorrhea, sneezing, nasal or ocular pruritus consistent with allergic rhinoconjunctivitis.

3.4.2. Criteria for safety of a given individual following challenge which would suspend the individual from further participation in the study will include:

1. No greater than 25% relative decrease in FEV₁ or FVC from WSP pre-challenge values, which does not improve within the first 2 hours of challenge.
2. FEV₁ must recover without treatment to within 90 % of baseline within 24 hours.
3. A symptom score no greater than 45 (representing a ranking of “moderate” on each of 15 criteria, with a maximum score of 60, see section 5.2.8. below) with improvement to a score of 15 or less within 6 hours without therapy.
4. Specifically, no symptom score greater than “moderate” (3 on a scale of 0-4) for shortness of breath or cough at 24 hours post-challenge.
5. Oxygen saturation of $\geq 93\%$ throughout the exposure period.
6. If albuterol therapy is needed more than once during an observation period.
7. Any significant abnormalities in PT and aPTT during the treatment periods will be assessed and reported to CDER, IRB, and the funding agency.

Criteria for safety within the entire protocol (failure of which would result in suspension of further study until consultation with the CDER of the FDA and the UNC IRB) will include the following:

1. The study will be suspended if 3 of the first 10 participants fail the individual safety criteria outlined above. If this occurs, the study will remain suspended until consultation with the CDER of the FDA.
2. Once 10 subjects have been enrolled, study suspension will occur if more than 25% of all participants fail the individual safety criteria outlined above
3. No occurrence of any SAE

Subjects will be under direct supervision for 6 hours from the start of WSP challenge and will have contact information for after-hours access to a study physician. In the event of an unexpected event, such as wheezing or bronchospasm, the physician will follow the usual medical standard of care to treat the subject.

4. Subject Selection and Withdrawal

Preliminary results from our screening WSP exposure study have shown that approximately 57% of healthy volunteers were responsive to the inflammatory effects of WSP. Based on this experience, we estimate we will need to screen 50 volunteers to identify 28 who are responsive to inhaled WSP. Anticipating an attrition rate of 20%, we will need to identify 35 volunteers for the intervention study, requiring an overall screen of a minimum of 64 volunteers. There will be no gender or ethnic restrictions. The target completion goal is 28 healthy volunteers and mild asthmatics. Individuals who meet all of the following criteria are eligible for enrollment as study participants.

4.1. Inclusion Criteria

1. Age 18-45 years, inclusive, of both genders
2. Negative pregnancy test for females who are not s/p hysterectomy with oophorectomy
3. FEV₁ of at least 75% of predicted (without use of bronchodilating medications for 12 hours), consistent with lung function of persons with no more than mild intermittent or mild persistent asthma.
4. Oxygen saturation of $\geq 93\%$ and blood pressure within the following limits: (Systolic between 150-85 mmHg, Diastolic between 90-50 mmHg).
5. Ability to provide an induced sputum sample.
6. Subject must demonstrate a $\geq 10\%$ increase in sputum neutrophils following inhaled WSP exposure, when compared to baseline sputum (to be completed in a separate protocol).
7. Ability/willingness to discontinue inhaled corticosteroids, montelukast, and cromolyn for 2 weeks without increased symptoms or increased need for beta agonist rescue medication prior to screening and through the course of the study.
8. Documented vaccine to Covid 19

4.2. Exclusion Criteria

Patients who meet *any* of these criteria are *not* eligible for enrollment as study participants:

1. Clinical contraindications:
 - a. Any chronic medical condition considered by the PI as a contraindication to the exposure study including significant cardiovascular disease, diabetes, chronic renal disease, chronic thyroid disease, history of chronic infections/immunodeficiency.
 - b. Viral upper respiratory tract infection within 4 weeks of challenge.

- c. Any acute infection requiring antibiotics within 4 weeks of exposure or fever of unknown origin within 4 weeks of challenge.
- d. Abnormal physical findings at the baseline visit, including but not limited to abnormalities on auscultation, temperature of 37.8° C, Systolic BP > 150mm Hg or < 85 mm Hg; or Diastolic BP > 90 mm Hg or < 50 mm Hg, or pulse oximetry saturation reading less than 93%.
- e. Physician directed treatment for an asthma exacerbation, including requirement for oral corticosteroids, within the preceding 12 months.
- f. Moderate or severe asthma
- g. Asthma symptoms more than 2 times a week, which would be characteristic of a person with moderate or severe persistent asthma.
- h. Daily requirement for albuterol due to asthma symptoms (cough, wheeze, chest tightness) which would be characteristic of a person with moderate or severe persistent asthma (not to include prophylactic use of albuterol prior to exercise)
- i. Requirement for asthma controller therapy greater than low dose ICS or leukotriene receptor antagonist. Persons requiring medium or high-dose ICS, ICS/LABA, ICS plus leukotriene receptor antagonists, omalizumab or other biologic therapies for asthma control will not be enrolled.
- a. Nighttime symptoms of cough or wheeze greater than 1x/week at baseline (not during a clearly recognized viral induced asthma exacerbation) which would be characteristic of a person of moderate or severe persistent asthma.
- b. History of intubation for asthma
- c. If there is a history of allergic rhinitis, subjects must be asymptomatic of allergic rhinitis at the time of study enrollment.
- d. Mental illness or history of drug or alcohol abuse that, in the opinion of the investigator, would interfere with the participant's ability to comply with study requirements.
- e. Cigarette smoking > 1 pack per month
- f. Unwillingness to use if sexually active (IUD, implant, sterilization, or when used in combination: birth control pills/patch and barrier methods). (i.e., those that, alone or in combination, result in a failure rate of <1% per year when used consistently and correctly). Note that male condom use, hormonal contraceptive pills, or hormonal contraceptive patches used alone have estimated failure rates that do not meet these criteria.
- g. Abnormal PT or aPTT values at screening or during the treatment period. Normal values will be those published by the clinical lab (Labcorp, INC).
- h. Use of immunosuppressive or anticoagulant medications including routine use of NSAIDS. Oral contraceptives are acceptable, as are Antidepressants and other medications may be permitted if, in the opinion of the investigator, the medication will not interfere with the study procedures or compromise safety and if the dosage has been stable for 1 month.
- i. Orthopedic injuries or impediments that would preclude bicycle or treadmill exercise.
- j. Inability to avoid NSAIDS, Multivitamins, Vitamin C or E or herbal supplements.
- k. Allergy/sensitivity to study drugs or their formulations
- l. Known hypersensitivity to methacholine or to other parasympathomimetic agents

- m. Unwillingness to avoid coffee, tea, cola drinks, chocolate, or other foods containing caffeine after midnight on the days that methacholine challenge testing is to be performed.
- n. Positive test for Covid 19 in the past 90 days

2. Pregnant/nursing women and children (< 18 years as this is age of majority in North Carolina) will also be excluded since the risks associated with woodsmoke exposure to the fetus or child, respectively, are unknown and cannot be justified for this non-therapeutic protocol. Individuals over 45 years of age will not be included due to the increased possibility of co-morbidities and need for prohibited medications.
3. Inability or unwillingness of a participant to give written informed consent.

